## 9.1 Dependent Variables (Endpoint Variables)

The efficacy endpoints detailed in sections 2.2.1 and 2.2.2 will serve as the dependent variables for the primary and secondary efficacy objectives of the final analysis respectively. Such endpoints will be utilized to meet the primary study objective, to establish the clinical performance of the VeSTAL device stimulation effect in subjects who are overweight.

#### 9.2 Independent Variables

Independent variables will be comprised of demographic randomisation stratification factors and baseline values for the relevant endpoint and will be utilised as covariates when investigating differences between treatment groups for the dependent primary efficacy endpoints.

Such endpoints will include:

- Gender (stratification factor)
- Baseline value, e.g. weight (kg), body fat (kg)

### 9.3 Examination of Subgroups

The following subgroups will be examined:

- Region [poolability analysis] (US, non-US)
- Gender (male, female)
- Age (<55 years, ≥55 years)

- Race (white, non-white)
- Ethnicity (Hispanic or Latino, not Hispanic or Latino/not reported)

Only subgroups with at least 10 patients per arm will be statistically evaluated. Some categories may be redefined or cut-offs changed as necessary to facilitate this.

## Neurovalens Limited Identifier: EXP18020

Clinical Study Identifier: 243973

Descriptive statistics (based on observed data) will be produced by subgroup for the primary efficacy (continuous weight and responders), key secondary efficacy for labelling claims, and primary safety (adverse event and adverse device effects) outcomes.

Interaction tests will be performed for the primary efficacy outcome where the subgroup main effect and a treatment\*subgroup interaction term will be added to the primary model for percentage weight loss. The p-value for the interaction term will be presented.

Individual subgroup analyses will be performed for the primary efficacy outcome model and a table and forest plot will be presented showing the individual subgroup results (LS means by treatment, difference in LS means and 95% confidence intervals), to evaluate the magnitude and nature of any differential treatment effects between subgroups.

If any subgroup interaction term shows p<0.1 or there is a difference between subgroups that is judged to be of a potentially clinically relevant magnitude then a multivariate model will also be fitted including additional covariates that may explain possible outcome differences between subgroups. Those additional covariates will include the other subgroup main effects and their interactions with treatment, and the interaction of baseline weight with treatment. The model parameter estimates, 95% CIs and p-values will be presented including the interaction terms.

Similar subgroup analyses will only be conducted for key secondary efficacy outcomes (for labelling claims) if there is evidence of a differential effect for the primary outcome.

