### Missing Data

The primary hypotheses will be tested on the intent-to-treat population. Missing data will be clearly reported and included in tables. We will assess the assumption that the data is missing completely at random. For the primary effectiveness analysis of total body weight loss (TBWL) as a continuous measure we will perform a multiple imputation analysis. We will include the same covariates in the multiple imputation model as in the linear regression, i.e. group, baseline total body weight, gender, age, study site. Two supportive sensitivity analyses with different approaches to imputing missing data will also be performed: last observation carried forward (LOCF) and baseline value carried forward (ie assuming no weight loss).

A sensitivity analysis will be performed with the binary weight loss endpoint. This analysis will include a bestcase scenario (assuming subjects with missing values have all lost over 5% body weight), a worst-case scenario (assuming no subjects with missing values have lost over 5% body weight), and a tipping point analysis (as described in Yan et al., 2009).

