### 10.2 Premature Withdrawal and Missing Data

All subjects enrolled into the study who meet the requirements for the ITT or Safety Analysis Set population will be included in the final analyses. This will include those subjects who withdrew from the study prematurely or have missing data.

For the large part, subjects will contribute what data they have available without imputation. However, for the primary efficacy endpoint of total body weight loss, three approaches to missing or incomplete data will be taken, under the assumption that the data is missing at random:

- 1. Multiple imputation will be applied by means of a multiple imputation model which is composed of three steps:
  - 1.1. The missing data are imputed multiple times to generate multiple sets of data. The imputed values are predicted total body weight loss values obtained from a linear regression model with observed total body weight loss data as the dependent endpoint, and the same covariates of interest that are used to adjust the primary endpoint (treatment group, gender and baseline weight). By providing 75 imputations per missing value, the variability between imputed values represents the uncertainty over the missing value.
  - 1.2. The 75 complete datasets are analyzed using the planned statistical analysis as per section 12.1.1. The results from the 75 complete datasets are then combined to produce an estimate for the primary endpoint, which reflects the uncertainty due to the missing values.
- 2. Last Observation Carried Forward (LOCF) will be applied for all subjects without data, inclusive of those who have withdrawn from the trial and subjects who have not reached the time point.
- 3. Baseline Observation Carried Forward (BOCF) will be applied for all subjects without data, inclusive of those who have withdrawn from the trial and subjects who have not reached the time point.

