## 12.1.1 Primary Efficacy Analyses

As the primary efficacy endpoints differ between regulatory clearance pathways, the primary efficacy analyses also differ accordingly.

For both the *EU and USA regulatory clearance pathways*, the primary efficacy endpoint will be summarized using summary statistics for the percentage weight loss at the 6 month time point. The mean percentage weight loss will also be presented graphically, by treatment group, over time. Summaries and graphical outputs will be produced for observed data unless specified otherwise..

For the continuous efficacy endpoint, mean percentage weight loss at 6 months, the difference between treatment groups will be assessed using a linear model controlling for covariates of interest: gender and baseline weight. The least square (LS) mean difference between groups will be assessed for a statistically significantly difference from 0 i.e. p-value <0.05. For the USA regulatory clearance pathway, the lower limit of the confidence interval of the LS Mean difference between groups will be assessed against the 2% target for a successful study, whereas the EU regulatory clearance pathway will assess whether the LS mean difference between groups is significantly different from zero. Analysis using multiple imputation for missing data will be primary, with the LOCF and BOCF imputation methods used for supportive analyses.

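### SAP 9.3 does not name the data for its subgroup and region interaction tests; run on the planned imputations, they would understate real differences

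*SAP*

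**What the plan says.** - **Test.** SAP 9.3 lists region (the poolability analysis), gender, age, race and ethnicity. It states: "Interaction tests will be performed for the primary efficacy outcome where the subgroup main effect and a treatment\*subgroup interaction term will be added". The model being extended is the main one for percentage weight loss. The p-value is presented, and each subgroup is also modelled separately for a table and forest plot.
- **What follows from it.** "If any subgroup interaction term shows p<0.1 or there is a difference between subgroups" large enough to be of possible clinical relevance, a multivariate model is fitted. It contains the other subgroup terms, their interactions with treatment, and treatment by baseline weight. Subgroup analyses of the labelling-claim endpoints are done only if the primary outcome shows a differential effect.
- **Data.** SAP 9.3 names a dataset once: "Descriptive statistics (based on observed data) will be produced by subgroup". It names none for the models. SAP 12.1.1 says of the primary model: "Analysis using multiple imputation for missing data will be primary". SAP 12.1.3 likewise uses imputation for weight outcomes and observed data for the rest.
- **Imputation model.** SAP 10.2 imputes from a linear regression on "the same covariates of interest that are used to adjust the primary endpoint (treatment group, gender and baseline weight"), and describes the number of draws thus: "By providing 75 imputations per missing value". A separate model is fitted for each time point. The protocol (section 34.1, Missing Data) has a longer list, "group, baseline total body weight, gender, age, study site", also without interactions.

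**The concern.** An imputation model should contain every term that the analysis model estimates. Here it omits the treatment-by-subgroup term for all five factors, and the main effect for all but gender. Every imputed value is therefore drawn as if the device effect were the same in US and non-US subjects, and in each age, race, ethnicity and gender group.

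Two things follow if the interaction is then fitted to those data. The estimate is pulled towards zero, and the Rubin standard error is too large for the spread that the pulled-in estimate actually has. Both make a real difference harder to see.

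At stake are the presented interaction p-values, the p<0.1 trigger for the multivariate model, and the condition for subgroup analyses of the labelling-claim endpoints. The forest plot is also affected if it uses the same imputations. The multivariate model inherits the problem, because treatment by baseline weight is missing from the imputation model too.

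**Working it through.** The documents give no power or error rate for the interaction tests, so there is no planned figure to reproduce. The sample-size inflation does reproduce: 180/(1 − 0.10) = 200.

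**Inputs from the documents.** N = 200 and 10% dropout (SAP 5). About 106 US and 94 non-US subjects (protocol section 6). SD 3.9 and a baseline correlation of 0.4 in size (protocol 34.3, Power Calculation, prints it as negative; SAP 5 as positive; the sign does not matter here). 75 imputations (SAP 10.2). Flag at p<0.1 (SAP 9.3). Residual SD = 3.9 × √(1 − 0.4²) = 3.574.

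**Assumptions, because the documents give no figure.** True interaction of 0, 2 or 3 percentage points. Dropout of 20% and 30% besides the planned 10%. Values missing completely at random.

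**Expected shrinkage.** Let θ be the true interaction, f the missing fraction in both regions, and s the non-US share of observed subjects. Take the US effect as reference.
- Imputed subjects in either region carry the pooled effect, sθ.
- The US effect becomes f·sθ, and the non-US effect (1 − f)θ + f·sθ.
- The difference is (1 − f)θ.

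For θ = 3 this gives 2.7, 2.4 and 2.1 at 10%, 20% and 30% missing. For θ = 2 it gives 1.8, 1.6 and 1.4.

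**Simulation.** 3,000 trials per scenario, Bayesian linear-regression imputation, Rubin's rules with small-sample degrees of freedom, two-sided test at p<0.1. Estimates are in percentage points.

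| Missing | True θ | SAP imputation: estimate | SAP imputation: flagged | Interaction in imputation: estimate | Interaction in imputation: flagged | Observed data: flagged |
|---|---|---|---|---|---|---|
| 10% | 0 | −0.02 | 6.7% | −0.02 | 9.7% | 9.6% |
| 10% | 2 | 1.78 | 49.3% | 1.99 | 57.1% | 57.0% |
| 10% | 3 | 2.71 | 82.0% | 3.02 | 86.8% | 87.1% |
| 20% | 0 | 0.03 | 4.5% | 0.04 | 10.2% | 10.0% |
| 20% | 2 | 1.61 | 38.1% | 2.02 | 54.0% | 54.5% |
| 20% | 3 | 2.41 | 70.7% | 3.03 | 82.7% | 82.9% |
| 30% | 0 | −0.01 | 2.2% | −0.02 | 9.9% | 10.0% |
| 30% | 2 | 1.38 | 25.2% | 1.99 | 49.0% | 49.9% |
| 30% | 3 | 2.09 | 55.7% | 3.02 | 79.1% | 79.6% |

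At 10% missing the power loss is 57.1 − 49.3 = 7.8 points for θ = 2, and 86.8 − 82.0 = 4.8 points for θ = 3.

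**Why the test is conservative.** At 10% missing with θ = 0, the mean Rubin standard error is 1.07 but the estimates have SD 0.97. The nominal cut-off of 1.645 then acts as 1.645 × 1.07/0.97 = 1.81, a two-sided tail of about 7%, in line with the simulated 6.7%.

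**Variants.**
- Region added to the imputation model as a main effect only (10% missing, θ = 3): estimate 2.71, flagged 82.5%. Restoring the protocol's study site would therefore not cure it.
- Unequal dropout, US 10% and non-US 30%, θ = 3: observed subjects are 106 × 0.9 = 95.4 and 94 × 0.7 = 65.8, so the pooled effect is 3 × 65.8/161.2 = 1.22. The expected estimate is 3 − 0.10 × 1.22 − 0.30 × (3 − 1.22) = 2.34; the simulation also gives 2.34. Flagged 68%, against 82% on observed data.
- A subgroup of 30 in 200, 10% missing, θ = 3: flagged 57%, against 64%.
- Imputation re-run separately within each region, θ = 2 (1,000 trials): difference recovered as 2.01 at 10% missing and 1.98 at 20%.

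**The case against.** **A reader might infer that these tests decide whether the regions may be pooled, and so that poolability would be declared too easily.** The documents do not support that. SAP 3 fixes in advance that all sites are analysed as one dataset. Protocol section 31 describes the poolability analysis as a check of comparability. Neither document has a declaration rule.

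**Use of imputed data is an inference.** That is correct. If SAP 9.3 means observed data, this bias is absent. But SAP 10.2 singles out the primary weight endpoint for imputation, and SAP 9.3 restricts only the descriptives to observed data. On either reading the dataset has to be stated.

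**The forest plot may not be affected.** This stands. SAP 9.3 does not say whether imputation is re-run within subgroups, and if it is, the shrinkage disappears.

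**There are safeguards.** In part. The observed-data descriptives by subgroup are free of this shrinkage, and a clinically relevant difference also triggers the multivariate model. That second trigger is weaker if it is read from estimates made on the same imputations.

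**At 10% dropout the loss is small, and power is low anyway.** This stands: even the corrected test flags a 2-point interaction only 57% of the time.

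**Observed-data regression needs data missing completely at random.** This does not stand. When only the outcome is missing, the regression is also valid if missingness depends on covariates in the model. The SAP 10.2 imputation gives no wider protection, since it uses only arm, gender and baseline weight at each time point.

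**Conclusion.** The point holds conditionally. If the SAP 9.3 interaction and subgroup models are fitted to the 75 datasets of SAP 10.2, evidence of a US/non-US or other subgroup difference is understated. At the planned dropout the effect is modest, on the assumed interactions of 2 to 3 points. It becomes material at the assumed 20% to 30%: a 3-point interaction is then flagged 71% and 56% of the time, against 83% and 79% with a matching imputation model. The size rests on the 106/94 split, the SD and correlation used for planning, and data missing completely at random.

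Two limits apply. For gender the main effect is already in the imputation model, so only its interaction is missing. The overall primary estimate and the success criteria do not use the subgroup terms and are unaffected. This is a cheap improvement to a secondary analysis and does not threaten the trial's main conclusion.

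**What to change.** Add one sentence to SAP 9.3 naming the data for the interaction, multivariate and individual subgroup models. Either choice works:

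1. Datasets imputed with that subgroup and its interaction with treatment in the imputation model. For the multivariate model, include all its interaction terms, treatment by baseline weight among them. Imputing separately by arm and subgroup is an alternative, though thin where a subgroup is near the minimum of 10 per arm.
2. Observed 6-month data, with those covariates in the analysis model.

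In the simulation both were unbiased and had nearly the same power. Adding region or site as a main effect alone is not enough.

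The first choice costs one extra imputation run per factor. The second needs no imputation, but its subgroup rows rest on a different set of subjects from the imputed overall estimate; an observed-data overall row in the forest plot would make them comparable. The primary analysis stays as written.

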### 9.4 Multiple Comparisons and Multiplicity

The primary efficacy endpoint, percentage total body weight loss from baseline will be assessed at the 6-month timepoint and therefore will not require any adjustment for multiplicity or multiple comparisons. As a result, to control the type I error rate, the threshold of significance will be set at the 5% alpha level, such that statistical significance will require p<0.05 (two-sided).

As the secondary endpoints analyzed with the intention of making a labelling claim will be assessed sequentially, with a predefined ordering, there will be no adjustments made to the alpha level for multiple testing.

If a significant difference is achieved for the primary endpoint at 6 months, the study will continue to assess the secondary endpoints in the following order: VAT loss, LDL, fat loss, lean muscle mass, atherogenic index, systemic inflammation, calorie intake and quality of life. Each endpoint can only be assessed if the criterion for the previous endpoints have been met and all endpoints will be assessed using a nominal alpha level of significance set at 5%.

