#### 1. INTRODUCTION

Neurovalens are conducting a randomized, double blind, sham controlled clinical trial to evaluate the efficacy and safety of non-invasive electrical vestibular nerve stimulation (VeNS), together with a lifestyle modification program, as a method of reducing excess body weight. The study will be randomized using a parallel assignment in a 1:1 active to control allocation, whereby the active group will use the vestibular nerve stimulation (VeNS) device, combined with a lifestyle modification program, and the control group will receive a sham device, combined with a lifestyle modification program. The study aims to recruit a total of 200 participants, across two or three sites, with a dropout allowance of 10% to generate a minimum of 90 active treatment and 90 control subjects. The study will be double blinded, meaning that both the subjects and outcome assessors will be blind to device assignment until the end of the visit at the 6 month timepoint.

For the purposes of the final analysis, the treatment assignment will be unblinded to all study personnel such that inferences can be made as to the efficacy and safety of the vestibular nerve stimulation (VeNS) device, in comparison to a sham control. The study will last approximately 6 months in total for each participant. The final analysis will be conducted at the 6 month timepoint. All subjects will cease involvement in the trial after the 6 month blinded period.

This document outlines the process followed by the study team to conduct the final analysis, along with the planned efficacy and safety analyses designed to fulfill the study objectives. As specified in the study protocol, it is noted that the criteria to meet the primary objective, to establish the clinical performance of the VeSTAL device stimulation effect in subjects who are overweight, differ between the EU and USA regulatory clearance pathways. As a result, this document clearly defines the proposed analyses and success criteria for both the EU and USA regulatory clearance pathways in the relevant sections. The secondary efficacy and safety objectives are shared by both regulatory pathways and therefore will follow the same analysis plan once the primary objective has been evaluated.

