## 2.2.2 Secondary Efficacy

The secondary efficacy endpoints will be consistent between regulatory clearance pathways and will include further analyses of percentage weight loss, fat loss, subject reported outcomes for quality of life, diet and activity, certain blood assays and changes in concomitant medications. These secondary endpoints will be analyzed at the 6 month timepoint.

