### 12.1.2 Supportive Primary Efficacy Analyses

For the purposes of the *USA regulatory clearance pathway*, the number and percentage of people achieving a loss of at least 5% of their body weight by the 6 month time point in the VeSTAL device treatment group will be presented with a two-sided 95% exact binomial confidence interval for the response rate. The criterion for success is that the lower bound of the 95% confidence interval of the response rate in the VeSTAL device group exceeds 50%. The analysis will use the multiple imputation for missing data as primary, with the LOCF and BOCF imputation methods as supportive.

A Fisher's exact test will also be used to compare the response rates in each treatment group and to detect whether the difference between groups is statistically significant. This will be repeated using multiple imputation, LOCF and BOCF methods for missing data. For the multiple imputation-based analysis, the median p-value approach will be used to generate the Fisher's exact test p-value (Eekhout 2017) and the exact confidence intervals described above will be produced using the imputation with a p-value equal to or nearest the median p-value.

In addition, a sensitivity analysis will be performed with the binary weight loss endpoint, to assess the impact of imputing the best and worst case scenarios for the binary response, when the total body weight loss at 6 months is missing. As per section 10.2, a tipping point analysis will also be utilised to demonstrate the level of imputation which changes the significance of the binary weight loss criterion.

No supportive primary efficacy analyses are required for the *EU regulatory clearance pathway*.

Identifier: EXP18020 Clinical Study Identifier: 243973

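### SAP 9.4 opens the label-claim sequence once weight loss differs from zero, without requiring the US or the EU success criteria

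*SAP*

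**What the plan says.** SAP 9.4 names one primary endpoint, percentage weight loss, tested at two-sided p<0.05, and then says: "If a significant difference is achieved for the primary endpoint at 6 months, the study will continue to assess the secondary endpoints". The order is VAT loss, LDL, fat loss, lean muscle mass, atherogenic index, systemic inflammation, calorie intake, quality of life, each at 5%. Within the sequence, "Each endpoint can only be assessed if the criterion for the previous endpoints have been met". SAP 12.1.1 supplies the null value: the LS "mean difference between groups will be assessed for a statistically significantly difference from 0".

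The success rules ask for more.

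- **US** (SAP 2.3.1, 12.1.1 and 12.1.2; Protocol 18.1): besides rejecting zero, "the lower limit of the confidence interval of the LS Mean difference between groups will be assessed against the 2% target", and success also requires that "the lower bound of the 95% confidence interval of the response rate in the VeSTAL device group exceeds 50" per cent. Protocol 18.1 makes both the mean and the categorical criterion necessary for a success claim.
- **EU** (SAP 2.3.1; Protocol 18.2 and 34.3): rejection of zero plus an observed mean difference of at least 2%. The EU clause of SAP 12.1.1 asks only for a difference from zero and leaves the 2% out.

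SAP 1 describes the secondary objectives as "shared by both regulatory pathways and therefore will follow the same analysis plan once the primary objective has been evaluated", and SAP 2.2.2 adds: "The secondary efficacy endpoints will be consistent between regulatory clearance pathways". SAP 2.2.2.1, SAP 2.3.2 and Protocol 18.3 place these endpoints after the primary endpoints; Protocol 18.3 leaves the details of the hierarchy to the SAP.

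**The concern.** The condition that opens the label-claim sequence is weaker than either pathway's definition of a successful trial. A trial can reject zero, miss the US margin or the US responder criterion, and still go on to test VAT loss and, after each success, the next endpoint. The plan bars a US success claim in that case. It does not say whether a significant VAT, LDL or fat-loss result may then support a US label claim. If the plan stays silent, that question can only be settled once results are known. The shared secondary plan in SAP 1, which follows once the primary objective has been evaluated rather than met, leaves the same gap.

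**Working it through.** **Inputs** (SAP 5; Protocol 34.3, Power Calculation): mean loss 6.6% active and 3.1% control, SD 3.9%, 180 participants 1:1 (90 per arm), correlation of baseline weight with weight loss 0.4 in the SAP and -0.4 in the protocol (the sign does not affect the adjusted standard error), 10% dropout. Complete data and normally distributed percentage loss are assumed here.

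**The plan's own figures.** 180/0.9 = 200 reproduces the recruitment target. The stated power above 80% for both US criteria does not reproduce under the confidence-limit rules (72% below). It does if the mean criterion is read as an observed 2% with p≤0.05 (86% together with the responder limit). The point does not depend on this; both figures are carried forward.

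**Thresholds, 90 per arm, adjusted.**
- SE = 3.9 × √(1 − 0.16) × √(2/90) = 0.533; t(0.975, 176) = 1.974.
- Sequence opens at an observed difference of 1.974 × 0.533 = 1.05 points.
- EU criterion: 2.00 points.
- US margin: 2 + 1.05 = 3.05 points.
- US responder criterion: the exact lower 95% limit exceeds 50% from 55/90 responders. The expected rate is 1 − Φ((5 − 6.6)/3.9) = 0.659, which gives power 0.858.

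**Single-criterion probabilities** (noncentral t): the sequence opens with probability 1.000 at a true difference of 3.5 and 0.962 at 2; the US margin passes with probability 0.80 and 0.025.

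**Joint probabilities.** 40,000 simulated trials per setting, linear model with group, baseline weight and sex, or unadjusted. EU met means significant with an observed difference of at least 2. At the planned effect:

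| Setting | Both US criteria met | Sequence open, US failed | of which EU met |
|---|---|---|---|
| 90 per arm, adjusted | 0.721 | 0.279 | 0.276 |
| 90 per arm, unadjusted | 0.676 | 0.324 | 0.319 |
| 100 per arm, adjusted | 0.763 | 0.237 | 0.236 |
| 100 per arm, unadjusted | 0.718 | 0.282 | 0.279 |

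Since the sequence opens in practically every trial at this effect, the third column is one minus the second. If the stated power above 80% is right, it is below 1 − 0.80 = 20%. In the first row, 0.276/0.279 = 99% of the affected trials meet the EU criterion.

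**Illustration at a true difference of 2%** (5.1% vs 3.1%, 90 per arm, adjusted; not a planned scenario): sequence open 0.959, both US criteria 0.006, so open with US failed 0.959 − 0.006 = 0.953. This splits into EU met 0.493 and neither pathway met 0.460. With means of 6.6% and 4.6% (control mean assumed) the figures are 0.934, 0.475 and 0.459. Across settings at this difference, neither pathway is met in 0.43 to 0.48 of trials.

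**The case against.** The best case for the plan is that the success criteria are already implied. Protocol 18.3 calls the testing hierarchical, after the primary endpoints in the plural; the US pathway has two; SAP 8 also uses the plural when pointing to 9.4; and 9.4 requires the criterion for previous endpoints to be met, a word the SAP uses elsewhere for the 2% and 50% rules. This reading is possible, but it does not settle the matter. The sentence just before that requirement sets the primary condition as a significant difference on weight loss alone. Section 9.4 never mentions the responder endpoint, and nothing says which pathway's criteria would apply. If the fuller reading was meant, the same edit is needed.

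For the EU, the 9.4 condition matches SAP 12.1.1 as worded. That stands, and it shows that the SAP disagrees with itself: 12.1.1 omits the 2% that SAP 2.3.1 and Protocol 18.2 and 34.3 require. Correcting 9.4 alone would leave that conflict.

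Three stronger readings are tempting and not supported.
- A reader might infer inflated type I error. The fixed sequence controls error at 5% for the zero null and the secondary endpoints.
- A reader might take 28% as the chance of a label claim, or of all eight tests being run. Opening the gate permits only the VAT test; each later test needs every earlier success, and the chance of a claim was not computed.
- A reader might infer that the plan permits a US success claim after a failed US primary. SAP 2.3.1 and Protocol 18.1 rule that out.

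**Conclusion.** The point holds as a gap between the gate and the success rules. As written, SAP 9.4 lets US label claims be tested when the US primary has failed, and lets the sequence start when the EU 2% criterion has failed. This rests on the wording and not on the simulation.

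Its practical weight depends on the true effect. At the planned effect the gap matters in about 28% of trials, or under 20% on the plan's stated power. The fix would stop the sequence altogether in only about 0.3% of trials (27.9 − 27.6 points); otherwise it decides which pathway a claim belongs to. At a true difference of 2%, about 95% of trials would enter the sequence after US failure, and in about 46% of trials it would run with neither pathway's criteria met. The figures assume complete data, normal percentage loss and the plan's SD and correlation. The change should be made, but it does not call the primary analysis into question.

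**What to change.** Rewrite SAP 9.4 with one gate per pathway.

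- **US:** the label-claim sequence is confirmatory only if, in the primary multiple-imputation analysis, the lower 95% limit of the LS mean difference exceeds 2% and the lower 95% limit of the active response rate exceeds 50%.
- **EU:** it is confirmatory only if p<0.05 in favour of the active device and the LS mean difference is at least 2%. The direction should be stated, because the present two-sided condition would also open on a result favouring sham.
- **Only the EU gate opens:** report the results as confirmatory for the EU and descriptive for the US.

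In SAP 1, keep the shared endpoints and models but change evaluated to met, by pathway. In SAP 12.1.1, add the 2% criterion to the EU clause so that it agrees with SAP 2.3.1 and Protocol 18.2 and 34.3.

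The cost is wording in three SAP sections, with no new data, model or sample size. The downside is that a pathway whose own primary criteria fail gets no confirmatory label claims. The US gate would also rest on the responder interval, which under SAP 12.1.2 "will be produced using the imputation with a p-value equal to or nearest the median p-value"; this change leaves that rule as it is.
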